7.2 Randomization

Random assignment to treatment arm is not being used in this study. Enrollment decisions will be determined by the site where the patient is enrolled as described in Section 6.1 of the protocol.

7.3 COVID-19 Pandemic Changes to Study Conduct

Table 8 below summarizes temporary changes to specific protocol assessments and procedures that are allowable during the COVID-19 pandemic (FDA-2020); these changes will not be recorded as protocol deviations unless otherwise specified. This appendix should be considered in effect until notification from Mirati is provided via Administrative Letter. Upon such notification, this appendix will no longer be applicable, and study conduct in accordance with the language in the body of the protocol will resume.

Patients should not be enrolled into the lead-in dose escalation portion of Cohort 9 unless they are able to meet the protocol defined assessments and procedures including adhering visit windows.

Table 8 COVID-19 Pandemic Changes to Study Conduct

Assessment/Procedure	Change During COVID-19 Pandemic
Visit Window	
 Visit windows of up to +/- 5 days are allowed for Day 1 (beyond Cycle 1) and Day 15 clinic visits.
Clinic Visits	
 Clinic visits may be conducted remotely by telephone/video conference; any missed assessments or procedures (e.g., tumor assessment, laboratory assessments, vital signs, study drug administration, etc.) should be documented as Protocol Deviations. Clinic visits may be conducted at the patient's residence by qualified home health care professionals; any missed assessments or procedures (e.g., laboratory assessments, vital signs, study drug administration, etc.) should be documented as Protocol Deviations.
Safety Laboratory Assessments	Safety laboratory assessments may be performed at the patients nearest CAP or CLIA certified local laboratory if a remote visit is being conducted, whenever feasible.
Nivolumab Dosing (for Cohorts 1 through 8)	
In order to reduce the need for Day 15 visits, Investigators should:
 
 Consider switching all patients who are on the Q2 week 240 mg nivolumab regimen to the Q4 week 480 mg regimen instead, as possible. Start all newly enrolled patients on the Q4 week 480 mg regimen.
Day 15 Sample Collection for PK and Other Exploratory Tests (for Cohorts 1 through 8)	
In order to eliminate the Day 15 clinic visit (for Cohorts 1 through 8):
 
 C1D15 PK samples, PD samples (TCR sequencing, flow cytometry, protein and cytokine biomarkers), and triplicate ECG may be collected at C2D1 instead. C2D15 PD samples (flow cytometry, protein and cytokine biomarkers) may be collected at C3D1 instead.
PK Sample Collections	
For Cohorts 1 through 8:
 
 The PK collection required post-dose at 7 hours (5-9 hours) on C1D1 and C1D15 may not be collected in order to reduce the time that patients need to remain in the clinic for the blood draw and ECGs.
PK sub-study for patients with renal impairment (for Cohorts 1 through 8)	Temporarily suspended for new patients to reduce the time patients need to remain in the clinic or hospital for blood draws.

Action and Reporting in the Event of Documented or Suspected COVID-19 Infection
Study Treatment

- Patients in Screening for Study Entry – Patients who exhibit symptoms consistent with COVID-19 infection or have recent COVID-19 test results consistent with active viral replication should delay

study entry and start of study treatment until resolution of symptoms and evaluation by the Investigator. Questions should be directed to the Sponsor's Medical Monitor.

- Patients in Study Treatment – For patients on study treatment exhibiting symptoms consistent with COVID-19 infection, contact the Sponsor's Medical Monitor as soon as feasible.

8.0 Analysis Populations

8.1 Screened Population

The Screened Population is defined as all patients who sign an informed consent for the study.

8.2 Enrolled Population

The enrolled population is defined as all patients who sign an informed consent form for the study and are determined by the investigator to meet all eligibility criteria during screening assessments. This population will be used to describe disposition and may include patients who have not received study treatment.

8.3 Full Analysis Set (FAS)

The full analysis set will include patients who receive at least one dose of each study treatment drug (i.e. at least one dose of both sitravatinib and nivolumab for Cohorts 1 through 8, or at least one dose each of sitravatinib, pembrolizumab and enfortumab for Cohort 9).

This population will be used to present OS and PFS analyses and will also be the population set used for tumor assessment, tumor response and time to event listings.

8.4 Clinical Activity Evaluable Population

Patients included in the clinical activity evaluable population are patients who receive at least one dose of each study treatment drug and have an evaluable baseline tumor assessment and at least one-post-baseline tumor assessment.

This population will be used to summarize tumor responses as well as to make decisions throughout the first two stages of the study on the Predictive Probability Design for Cohorts 1 through 6.

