9.3 Analysis Populations

9.3.1 Full Analysis Population

The full analysis population (FAP) is defined as all patients who receive one dose of all study treatments (i.e. at least one dose of both sitravatinib and nivolumab for Cohorts 1 through 8, or at least one dose each of sitravatinib, pembrolizumab and enfortumab for Cohorts 9 and 10).

The primary efficacy analyses of the primary and secondary efficacy endpoints will be performed in the FAP for all cohorts. In addition, the FAP population will be used 1) in making decisions to expand the study to the third stage of enrollment for Cohorts 1 through 4, and 2) for the interim futility analysis for Cohorts 7 and 8.

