In the event that results in the initial study cohorts are of high interest for efficacy, one or more cohorts in patients with documented disease progression on or after a PD-(L)1 checkpoint inhibitor therapy and an antibody-drug conjugate (ADC; e.g. enfortumab vedotin, sacituzumab govitecan), in any order or in combination together. Decisions for implementation of additional cohorts in the study will be made in collaboration with the Investigators and documented for Regulators and Institutional Review Boards by an Administrative Letter to Investigators.

Based on the evolving treatment landscape of urothelial carcinoma in particular with the clinical activity of ADCs, and early efficacy and safety results from active study cohorts, and in consult with Investigators, both Cohort 7 and Cohort 8 described in this section were implemented by an Administrative Letter dated September 2019.

The ORR using taxanes in the population of advanced/metastatic urothelial carcinoma who have previously received treatment with a checkpoint inhibitor therapy and ADC is assumed to be 10%; thus, this rate is considered uninteresting. The design for Cohort 7 and Cohort 8 will utilize a 95% confidence interval to exclude an ORR of 10%. Assuming sitravatinib in combination with nivolumab treatment will result in an ORR of at least 25% in this treatment setting, a sample size of approximately 55 evaluable patients would be sufficient for the lower bound of a 2-sided 95% confidence interval (Clopper-Pearson method) to exclude an ORR of 10%.

The design will include a non-binding stopping rule for futility derived using East[®] software v6.5 to control the Type 2 error rate of 0.117. The Type 2 error spending function is based on the Rho family with parameter 2.0. The futility analysis will be conducted when approximately 17 evaluable patients (approximately 30% of the total number of patients) are available for the response assessment. The futility bound will be 1 or fewer observed responses among the first 17 patients.

7.1.5.5 Cohort 9:

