SD	CR	SD
SD	PR	SD
SD	SD	SD
SD	NE	SD or NE (2)
First Time Point Response**	Second Time Point Response	Confirmed Response (Best Response)*
NE	CR	SD
NE	PR	SD
NE	SD	SD
NE	NE	NE

* A Best Response of SD can only be made after the patient is on-study for a minimum of six (6) weeks (42 days). If the patient is on-study less than six (6) weeks (42 days), any tumor assessment indicating stable disease before this time period will have a Best Response of NE unless PD is identified.

** Subsequent documentation of CR may provide confirmation of a previously identified CR for patients where the second integrated response was NE. Subsequent documentation of PR may provide confirmation of a previously identified PR for patients where the second integrated response was NE or SD. If the third Time Point Response (TPR) confirms the CR (or PR) then the Confirmed Response will be CR (or PR). For this study, only one (1) intervening NE is allowed between CRs/PRs. For example: CR NE CR = CR; PR NE PR = PR. Additionally, one (1) SD is allowed between PRs (e.g., PR SD PR = PR).

(1) Best response will be SD if the first TPR is after at least six (6) weeks (42 days) on-treatment. Otherwise, the best response will be PD.

- (2) Best response will be SD if the first TPR is after six (6) weeks (42 days) on-study. Otherwise, the best response will be NE.
- (3) TPR is SD if the increase from the first to the second assessment does not qualify for PD.

For patients with unconfirmed CR/PR and who subsequently drop off the study, the best overall response will be SD.

Descriptive statistics (frequency, percentage) for best overall response (CR, PR, SD, PD, NE) based on response assessments by the investigator will be presented.

The primary analysis will be conducted in the Full Analysis Population and supportive analysis will be presented in the Clinical Activity Evaluable population.

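### Cohorts 7/8: the 10% exclusion and its Type 2 error are stated for 55 evaluable patients, but the primary ORR interval uses the full analysis set; exact power is 0.845 at N = 55, not 0.883, and lower if patients are non-evaluable

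*SAP*

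**What the plan says.** **Primary population for ORR.** Protocol 9.3.1: "The primary efficacy analyses of the primary and secondary efficacy endpoints will be performed in the FAP for all cohorts". SAP 11.6.1: "The primary analysis will be conducted in the Full Analysis Population and supportive analysis will be presented in the Clinical Activity Evaluable population". In both documents this set is every patient with at least one dose of each study drug.

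**Section 8 of the SAP.** Of the full analysis set, SAP 8.3 says "This population will be used to present OS and PFS analyses" and adds listings; it does not name the ORR analysis. Of the evaluable set, SAP 8.4 says "This population will be used to summarize tumor responses as well as to make decisions". That sentence goes on to limit the decisions to the first two stages of the Predictive Probability Design in Cohorts 1 to 6. Evaluable patients need, beyond dosing, an evaluable baseline and at least one post-baseline tumor assessment.

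**Criterion for Cohorts 7 and 8.** SAP 7.1.5.4, like Protocol Appendix 8, says the ORR under taxanes "is assumed to be 10%; thus, this rate is considered uninteresting". It assumes that the combination "treatment will result in an ORR of at least 25% in this treatment setting", and concludes that "a sample size of approximately 55 evaluable patients would be sufficient for the lower bound of a 2-sided 95% confidence interval" to lie above 10%. A non-binding futility rule (1 or fewer responses in the first 17 patients) is attached to a Type 2 error of 0.117.

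Neither section converts 55 evaluable patients into a number for the full analysis set, gives a non-evaluable rate, or says which population's interval must exclude 10%. SAP 11.6.1, which names the population, carries an exact test against 5%, not 10%.

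**The concern.** The criterion and the primary analysis count different patients. A patient who receives both drugs but has no evaluable post-baseline scan is in the full analysis set denominator and cannot have a confirmed response. Each such patient lowers the observed ORR and its lower bound without any change in the number of responders. A cut-off and power worked out for 55 evaluable patients therefore need not apply to the interval that is reported as primary.

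At stake is whether the stated Type 2 error describes the analysis that will be done, and whether a borderline count meets the criterion.

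**Working it through.** **Inputs.** Rate to exclude p0 = 10%, assumed ORR p1 = 25%, N = 55, two-sided 95% Clopper-Pearson interval, Type 2 error 0.117, futility at 1 or fewer of 17 (all SAP 7.1.5.4 and Protocol Appendix 8). The non-evaluable share is not in the documents; 0 to 20% is assumed.

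**Step 1: the plan's own figure.** 1 − 0.117 = 0.883. A one-sample normal approximation with null variance and one-sided 0.025 gives power

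Φ{[(p1 − p0)√N − 1.96√(p0(1 − p0))] / √(p1(1 − p1))}.

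At N = 55 this is Φ{(0.15 × 7.416 − 1.96 × 0.3)/0.433} = Φ(1.211) = 0.887, a Type 2 error of 0.113. At N = 54 it is 0.1175. So 0.117 is recovered approximately, but only under the normal approximation.

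**Step 2: the exact rule at N = 55.** The lower bound for x of n is the 2.5% quantile of Beta(x, n − x + 1).

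- 10/55: 9.08%, fails.
- 11/55: 10.43%, passes. The cut-off is 11.
- 14/55, about the expected count at 25%: 14.67%. In that sense 55 is sufficient, as the plan says.
- Exact power P(Bin(55, 0.25) ≥ 11) = 0.845, a Type 2 error of 0.155. If the futility rule is obeyed, power is 0.821 and the Type 2 error 0.179.
- Exact one-sided error P(Bin(55, 0.10) ≥ 11) = 0.019.

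**Step 3: 11 responders in a larger full analysis set.**

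| Full analysis set | Lower bound for 11 responders | Excludes 10%? |
|---|---|---|
| 55 | 10.43% | yes |
| 56 | 10.24% | yes |
| 57 | 10.05% | yes |
| 58 | 9.87% | no |
| 60 | 9.52% | no |

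The change comes with the third non-evaluable patient (3/58 = 5.2%).

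**Step 4: power when 55 are evaluable, 25% of them respond, and the rest of the full analysis set cannot.** Power = P(Bin(55, 0.25) ≥ cut-off), before any futility stop.

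| Non-evaluable patients | Full analysis set | Cut-off | Power |
|---|---|---|---|
| 0 to 2 | 55 to 57 | 11 | 0.845 |
| 3 to 9 | 58 to 64 | 12 | 0.754 |
| 10 to 14 | 65 to 69 | 13 | 0.643 |

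Assumed shares of 5% and 10% give sets of 58 and 61; 15% and 20% give 65 and 69.

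**Step 5: 55 as the size of the full analysis set.** The cut-off is 11. Power is 0.845 if 25% is the ORR in that set. If 25% applies only to the evaluable and three of the 55 are not evaluable, power is P(Bin(52, 0.25) ≥ 11) = 0.785.

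**The case against.** **The primary population is clear.** From SAP 8.3 and 8.4 a reader might infer that the SAP names two primary populations for ORR. It does not. SAP 11.6.1 and Protocol 9.3.1 agree, SAP 11.6.1 labels the evaluable analysis supportive, and summarizing responses in the evaluable set fits that label. The omission of ORR in SAP 8.3 is an editorial gap. This objection stands in full.

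**No text gives the Cohort 7/8 decision to the evaluable set.** A reader might go on to infer an inflated false-positive rate from a decision on that set. The decisions in SAP 8.4 concern Cohorts 1 to 6 only, and Protocol 9.3.1 assigns even the Cohort 7/8 futility look to the full analysis population. That inference has no basis in the documents.

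**Fifty-five may already be the cohort total.** The Study Summary allows up to 345 patients in Cohorts 3 to 9, and 2 × 40 + 2 × 45 + 2 × 55 + 30 + 35 = 345. On that count a full analysis set of 58 or more is not budgeted, and 11 responders pass in either population (11/55 gives 10.43%, 11/52 gives 11.06%). This stands in part: both sizing sections still say evaluable, so the documents leave the basis open, and the gap between 0.883 and 0.845 remains on this reading too.

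**The thresholds lie on rounding edges.** A 5% share gives 55/0.95 = 57.9, just at the change; at 57 nothing happens. That is fair, and the result should be read as steps in the count of non-evaluable patients, not as a prediction.

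**Conclusion.** The criterion for Cohorts 7 and 8 and its Type 2 error are stated on a basis that is not that of the primary analysis, and 0.117 is not what the Clopper-Pearson rule delivers. With 55 patients, all evaluable, and a 25% ORR, exact power is 0.845 (0.821 with the futility rule obeyed) against an implied 0.883. This part needs no assumption about evaluability.

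The further loss, to 0.754 or 0.643, rests on two assumptions: that 55 counts evaluable patients and the full analysis set is larger, and that 25% is the ORR among the evaluable. With 0 to 2 non-evaluable patients the cut-off stays at 11. The documents give no rate from which to say how likely three or more are. A reader might infer that the conclusion for these cohorts is likely to turn on the denominator; the documents do not support that, since only borderline counts are affected.

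**What to change.** In SAP 7.1.5.4 and Protocol Appendix 8, state that the 10% exclusion is judged on the Clopper-Pearson interval in the full analysis set. Then take one of two routes:

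- express the 55 as full analysis set patients, which agrees with the 345-patient ceiling, with a cut-off of 11 and exact power of about 0.84, and say that the 25% refers to that set; or
- keep 55 evaluable patients, state an assumed non-evaluable rate, and give the cut-off and exact power for the resulting full analysis set (for example 12 responders and 0.754 at 58 to 64).

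On either route, replace 0.117 by the exact Type 2 error, with and without the futility rule.

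Two consistency edits go with this: list the ORR analysis under the full analysis set in SAP 8.3, and call the response summary in SAP 8.4 supportive.

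The cost is wording and a short recalculation. The first route needs no extra patients. The stated power becomes less favourable.

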8.5 Safety Population

The safety population is defined as all patients who received at least 1 dose of any study treatment (sitravatinib, nivolumab, pembrolizumab or enfortumab). The Safety population will be used for all safety analyses.

8.6 Molecular Marker Evaluable Population

The molecular marker evaluable population will consist of all patients who receive at least one dose of any study treatment (sitravatinib, nivolumab, pembrolizumab or enfortumab) and for whom PD-L1 expression or circulating PD-L1 results are available.

8.7 Pharmacokinetic Evaluable Population

The pharmacokinetic evaluable population will consist of all patients who received treatment with sitravatinib and had sufficient concentration-time data to permit calculation of PK parameters for sitravatinib. For patients who were noncompliant with respect to administration of sitravatinib, or for patients with incomplete data, a decision as to their inclusion in the analysis will be made on a case-by-case basis.

8.8 Pharmacodynamic Evaluable Population

The pharmacodynamic evaluable population will consist of all patients who receive at least one dose of any study treatment (sitravatinib, nivolumab, pembrolizumab or enfortumab) and for whom PD results are available.

8.9 DLT Evaluable Population (only applicable to lead-in dose escalation portion of Cohort 9)

The DLT evaluable population is defined as patients enrolled in the lead-in dose escalation portion of Cohort 9, who experienced a DLT or who cleared the DLT period. Patients who received prohibited therapy during Cycle 1 (refer to Section **Error! Reference source not found.**), or who did not take at least 80% of the planned dose of sitravatinib, and 1 planned dose of pembrolizumab and 2 planned doses of enfortumab in Cycle 1 will be ineligible for DLT evaluation and will be replaced unless they experience a DLT event. The DLT evaluable population will be used for dose escalation decisions during the lead-in dose escalation evaluation.

9.0 Data Handling

Listings of all patient data will be prepared. Data summaries will be presented in tabular and/or graphical format and summarized descriptively, where appropriate.

For all variables, only the observed data from patients will be used in the statistical analyses; there is no plan to estimate missing data. Patients without a valid clinical response assessment will be assigned a best overall response of not evaluable (NE). Data from patients who are lost to follow-up or have missing observations before reaching an endpoint in any of the time-to-event analyses will be treated as censored with specific rules defined in the SAP.

9.1 Imputation of AEs or Concomitant Medications

Start Date

If the start date of AE is completely missing (i.e., the day, month, and year are all unknown), the start date will be set to the date of first dose of study medication. No imputation will be performed for medications with completely missing start dates.

Missing Day Only

- If the month and year of the incomplete date are the same as the month and year of the **first dose date**, then the day of the **first dose date** will be assigned to the missing day.
- If either the year is before the year of the **first dose date** or if years are the same but the month is before the month of the **first dose date**, then the last day of the month will be assigned to the missing day.
- If either the year is after the year of the **first dose date** or if both years are the same but the month is after the month of the **first dose date**, then the first day of the month will be assigned to the missing day.

Missing Month Only

- The day will be treated as also missing and both month and day will be replaced according to the below procedure.

Missing Day and Month

- If the year of the incomplete date is the same as the year of the **first dose date**, then the day and month of the **first dose date** will be assigned to the missing fields.

- If the year of the incomplete date is not the same as the year of the **first dose date**, then January 1 will be assigned to the missing fields.
- If the stop date is complete and the imputed start date is after the stop date, then the start date will be imputed using the stop date.

Stop Date

Missing Day Only

- If the month and year of the incomplete date are the same as the month and year of the **last visit date**, then the day of the **last visit date** will be assigned to the missing day.
- If either the year is before the year of the **last visit date** or if both years are the same but the month is before the month of the **last visit date**, then the last day of the month will be assigned to the missing day.
- If either the year is after the year of the **last visit date** or if both years are the same but the month is after the month of the **last visit date**, then the first day of the month will be assigned to the missing day.

Missing Month Only

- The day will be treated as missing and both month and day will be replaced according to the below procedure.

Missing Day and Month

- If the year of the incomplete date is the same as the year of the **last visit date**, then the day and month of the **last visit date** will be assigned to the missing fields.
- If the year of the incomplete date is before the year of the **last visit date**, then December 31 will be assigned to the missing fields.
- If the year of the incomplete date is after the year of the **last visit date**, then Jan 1 will be assigned to the missing fields.

9.2 Imputation of Alternative Cancer Treatment Start Date

If the start date is completely missing, given that the patient did receive the anti-cancer therapy, the start date will be set to last dose date + 1.

Missing Day Only

- If the month and year of the incomplete date are the same as the month and year of the last dose date, then the last dose date + 1 will be assigned to the missing day.
- If the month and year of the incomplete date are after the month and year of the last dose date, then the first day of the month will be assigned to the missing day.

Missing Month Only

- The day will be set as missing and treated as missing Day and Month.

Missing Day and Month

- If the year of the incomplete date is the same as the year of the last dose date, then the last dose date + 1 will be assigned to the missing day and month.
- If the year of the incomplete date is after the year of the last dose date, then Jan 1 will be assigned to the missing day and month.

